2.1.3 Efficacy endpoints

Efficacy endpoints include lipid parameters (ie, Total-C, LDL-C, HDL-C, fasting TG, non-HDL-C, Apo B, Apo A-1, ratio Apo B/Apo A-1, Lp[a]). All these parameters are measured or calculated by a central laboratory, for both scheduled and unscheduled time points. Calculated LDL-C is obtained using the Friedewald formula. However if TG values exceed 400 mg/dL (4.52 mmol/L), the LDL-C should be measured by the Central Laboratory (via beta quantification method) and used as the reference value for LDL-C rather than calculated LDL-C. Non-HDL-C is calculated by subtracting HDL-C from the Total-C.

Unless otherwise specified, all lipid values (scheduled or unscheduled, fasting or not fasting) may be used to provide a value for the primary and secondary efficacy endpoints. All measurements, scheduled or unscheduled, fasting or not fasting, will be assigned to analysis windows defined in Section 2.5.4, Table 5 and Table 6 in order to provide an assessment for time points when the lipid values were to be collected as per protocol. For TG, only fasting measurements will be used and measurements with missing fasting status will be excluded from the analyses.

For all time points post-baseline, the value used for the analyses at a given time point (eg, at Week 24) is the value obtained within the corresponding analysis window.

The baseline definition described in Section 2.1.1 will be used for the analyses of the double-blind and OL periods.

The analysis of primary and key secondary endpoints consists of the comparison of each alirocumab dosing regimen group versus its contemporaneously randomized placebo group (ie, alirocumab Q2W versus placebo Q2W; alirocumab Q4W versus placebo Q4W) for endpoints listed in primary endpoint and secondary endpoints. A sequential inferential approach will be used within each regimen (refer to Section 2.4.4.3).

2.1.3.1 Primary efficacy endpoint(s)

The primary efficacy endpoint is the percent change in LDL-C from baseline to Week 24 in the intent-to-treat (ITT) population (defined in Section 2.3.1.1), using LDL-C values regardless of adherence to treatment (ITT estimand). Primary endpoint is defined as: 100x (LDL-C value at Week 24 - LDL-C value at baseline) / LDL-C value at baseline.

The LDL-C at Week 24 will be the LDL-C level obtained within the Week 24 analysis window. All calculated and measured LDL-C values (scheduled or unscheduled, fasting or not fasting) may be used to provide a value for the primary efficacy endpoint if appropriate according to the above definition. In case both calculated and measured LDL-C values are provided for the same sampling, the measured LDL-C will be considered.

2.1.3.2 Secondary efficacy endpoint(s)

2.1.3.2.1 Key secondary efficacy endpoints

The key secondary efficacy endpoints are:

- Percent change in LDL-C from baseline to Week 12 (ITT estimand).
- Percent change in Apo B from baseline to Week 24 (ITT estimand).
- Percent change in non-HDL-C from baseline to Week 24 (ITT estimand).
- Percent change in Total-C from baseline to Week 24 (ITT estimand).
- Percent change in Apo B from baseline to Week 12 (ITT estimand).
- Percent change in non-HDL-C from baseline to Week 12 (ITT estimand).
- Percent change in Total-C from baseline to Week 12 (ITT estimand).
- Proportion of patients achieving a LDL-C level lower than 130 mg/dL (3.37 mmol/L) at Week 24 (ITT estimand).
- Proportion of patients achieving a LDL-C level lower than 130 mg/dL (3.37 mmol/L) at Week 12 (ITT estimand).

- Proportion of patients achieving a LDL-C level lower than 110 mg/dL (2.84 mmol/L) at Week 24 (ITT estimand).
- Proportion of patients achieving a LDL-C level lower than 110 mg/dL (2.84 mmol/L) at Week 12 (ITT estimand).
- Percent change in Lp (a) from baseline to Week 24 (ITT estimand).
- Percent change in Lp (a) from baseline to Week 12 (ITT estimand).
- Percent change in HDL-C from baseline to Week 24 (ITT estimand).
- Percent change in fasting TG from baseline to Week 24 (ITT estimand).
- Percent change in Apo A-1 from baseline to Week 24 (ITT estimand).
- Percent change in HDL-C from baseline to Week 12 (ITT estimand).
- Percent change in fasting TG from baseline to Week 12 (ITT estimand).
- Percent change in Apo A-1 from baseline to Week 12 (ITT estimand).

2.1.3.2.2 Other secondary efficacy endpoints

- All primary and key secondary endpoints in the modified ITT (mITT) population (defined in Section 2.3.1.2), using LDL-C values during the treatment period (on-treatment estimand).
- Absolute change in Apo B/Apo A-1 ratio to Week 12 and Week 24 (ITT and on-treatment estimands).
- Proportion of patients achieving at least 30% reduction, 50% reduction in LDL-C at Week 24 (ITT and on-treatment estimands).
- Proportion of patients achieving at least 30% reduction, 50% reduction in LDL-C at Week 12 (ITT and on-treatment estimands).
- Percent change in LDL-C from baseline to Week 104 (ITT and on-treatment estimands).

2.1.3.2.3 Exploratory endpoint of the FMD sub-study

The exploratory endpoint of the FMD sub-study is the absolute change from baseline to Week 24 in flow mediated dilatation of the brachial artery (as determined by the central reading laboratory) regardless of adherence to treatment. The analysis will consist of the comparison of alirocumab to placebo, regardless of the dosing regimen cohort.

On-treatment analysis will be also conducted.

2.1.4 Safety endpoints

The safety analysis will be based on the reported AEs and other safety information, such as clinical laboratory data, vital signs, Tanner stage and Cogstate battery (neurocognitive functions) test assessment.

Observation period for the Q2W dosing regimen cohort,

The observation of safety data will be as follows:

- The pre-treatment period is defined from the signed informed consent up to the first dose of double-blind IMP.
- Double-blind treatment-emergent adverse event (TEAE) period is defined as:
 - the time from the first dose of double-blind IMP to the last dose of double-blind IMP injection +70 days (10 weeks) as residual effect of alirocumab is possible until 10 weeks after the stop of treatment IMP injection. This period will be truncated at the first dose of open-label IMP for patients proceeding into the OL treatment period.

The double-blind TEAE period will include:

- The double-blind treatment period defined as the time from the first dose of doubleblind IMP injection up to the day of last dose of double-blind IMP injection +21 days.
- The double-blind post-treatment period is defined as the time starting the day after the end of the double-blind TEAE period (truncated at the first dose of open-label IMP for patients proceeding into the open-label treatment period).
- The open-label TEAE period is defined as the time from the first dose of open-label IMP injection up to the day of last dose of open-label IMP injection +70 days.
 - The open-label TEAE period will include the open-label treatment period defined as the time from the first dose of open-label IMP injection up to the day of last dose of open-label IMP injection + 21 days.
- The open-label post-treatment period is defined as the time starting the day after the end of the open-label TEAE period (ie, 71 days after the day of last dose of open-label IMP injection).

Observation period for the Q4W dosing regimen cohort,

The observation of safety data will be as follows:

- The pre-treatment period is defined from the signed informed consent up to the first dose of double-blind IMP.
 - Double-blind treatment-emergent adverse event (TEAE) period is defined as: the time from the first dose of double-blind IMP to the last dose of double-blind IMP injection +70 days (10 weeks) as residual effect of alirocumab is possible until 10 weeks after the stop of treatment IMP injection. This period will be truncated at the first dose of open-label IMP for patients proceeding into the OL treatment period.

The double-blind TEAE period will include:

- The double-blind treatment period defined as the time from the first dose of doubleblind IMP injection up to the day of last dose of double-blind IMP injection +35 days for patients who stopped definitively the IMP before the switch to Q2W regimen (actual or sham) at Week 12

- The double-blind treatment period defined as the time from the first dose of doubleblind IMP injection up to the day of last dose of double-blind IMP injection +21 days, otherwise.
- The double-blind post-treatment period is defined as the time starting the day after the end of the double-blind TEAE period (truncated at the first dose of open-label IMP for patients proceeding into the open-label treatment period).
- The open-label TEAE period is defined as the time from the first dose of open-label IMP injection up to the day of last dose of open-label IMP injection +70 days.

The open-label TEAE period will include the open-label treatment period defined as:

- the time from the first dose of open-label IMP injection up to the day of last dose of open-label IMP injection +35 days, for patients still under Q4W regimen at the end of the open-label treatment period.
- the time from the first dose of open-label IMP injection up to the day of last dose of open-label IMP injection + 21 days, otherwise.
- The open-label post-treatment period is defined as the time starting the day after the end of the open-label TEAE period (ie, 71 days after the day of last dose of open-label IMP injection).

2.1.4.1 Adverse events variables

Adverse events (including serious adverse events (SAEs) and adverse events of special interest (AESIs) are recorded from the time of signed informed consent until the end of study (definition of AESIs is provided in the study protocol). All AEs diagnosed by the Investigator will be reported and described.

All AEs will be coded to a "lowest level term (LLT)", "preferred term (PT)", "high level term (HLT)", "high level group term (HLGT)" and associated primary "system organ class (SOC) using the version of MedDRA currently in effect at Sanofi at the time of database lock.

Adverse event observation period

- Pre-treatment AEs are AEs that developed or worsened or became serious during the pre-treatment period.
- For double-blind period:
 - Double-blind treatment-emergent adverse events are AEs that developed or worsened or became serious during the double-blind TEAE period.
 - Double-blind post-treatment AEs are AEs that developed or worsened or became serious during the double-blind post-treatment period.
- For open-label period:

- Open-label treatment-emergent adverse events are AEs developed or worsened or became serious during the open-label TEAE period.
- Open-label post-treatment AEs are AEs that developed or worsened or became serious during the open-label post-treatment period.

Groupings of adverse events

Grouping of adverse events include the following:

- Local injection site reactions (AESIs or not), selected using e-CRF specific tick box on the adverse event page.
- General allergic events (AESIs or not), selected using SMQ "hypersensitivity" (broad and narrow) excluding the preferred terms linked to local injection site reactions (ie, preferred terms containing "injection site" or "infusion site").
- ALT >3 ULN (if baseline ALT < ULN), or ALT ≥2 times the baseline value (if baseline ALT ≥ ULN), selected using laboratory data.
- Neurologic events (AESIs or not), selected using a CMQ based on SMQs "demyelination" (broad and narrow), "peripheral neuropathy" (broad and narrow), and "Guillain-Barre syndrome" (broad and narrow) excluding the following preferred terms "acute respiratory distress syndrome", "asthenia", "respiratory arrest" and "respiratory failure" and including selected PTs from SMQ "optic nerve disorders" (see Table 8 for the list of terms).
- Neurocognitive events:
 - Selected using a CMQ, based on the following 5 HLGTs: "deliria (including confusion)", "cognitive and attention disorders and disturbances", "dementia and amnestic conditions", "disturbances in thinking and perception", and "mental impairment disorders".
 - A second grouping of terms for neurocognitive events was defined based on Regulatory Agency request (see Table 9 for the list of terms).
- Symptomatic overdose of IMP selected using appropriate MedDRA codes and the tick boxes "Overdose of Alirocumab" and "Symptomatic Overdose" in the overdose adverse event form.
- Pregnancy (including male patient's partner) selected using eCRF tick box.

In addition, the following additional grouping of events will be provided:

- Hepatic disorder events using SMQ "Hepatic disorder".
- Diabetes mellitus or diabetic complications using 1/HLGT "diabetes complications" (including PTs pertaining to the secondary SOC included in the HLGT), 2/ the HLT "diabetes mellitus", 3/ the HLT "carbohydrate tolerance analyses (including diabetes)" excluding PTs "blood glucose decreased" and "glycosylated haemoglobin decreased" and 4/ from the HLT "hyperglycaemic conditions NEC" only the following PTs "hyperglycaemia", "hyperglycaemic unconsciousness" and "hyperglycaemic seizure".

• Cataract using HLT "Cataract conditions".

Of note, groupings are based on the version of MedDRA currently in effect at Sanofi at the time of this SAP version (Version 23.1) and may be updated if appropriate, based on a more recent version available at time of database lock.

2.1.4.2 Deaths

The deaths observation periods are per the observation periods defined above.

For double-blind period:

- Death on-treatment: deaths occurring during the double-blind TEAE period,
- Death post-treatment: deaths occurring during the double-blind post-treatment period

For open-label period:

- Death on-treatment: deaths occurring during the open-label TEAE period,
- Death post-treatment: deaths occurring during the open-label post-treatment period

2.1.4.3 Laboratory safety variables

Clinical laboratory data consist of blood analysis, including hematology and clinical chemistry. Clinical laboratory values will be analyzed into international units. International units will be used in all listings and tables. Clinical laboratory values converted into conventional (US) units will be also available in the database. Analyses can be provided upon request.

Unless otherwise specified below, blood samples for clinical laboratories (eg, hematology, clinical chemistry) were to be collected during:

- Screening at Visit 2 (up to Week -2).
- The double-blind period at Visit 4 (Week 0 / Day 1), Visit 6 (Week 12) and Visit 7 (Week 24) /or early termination.
- The OL period at Visit 8 (Week 32), Visit 9 (Week 44), Visit 11 (Week 68) and Visit 14 (Week 104)/or early termination, for patients proceeding into OL period.

Adrenal gland hormones, gonadal and pituitary hormones, fat soluble vitamins, were to be collected during:

- The double-blind period at Visit 4 (Week 0 / Day 1) and Visit 7 (Week 24)/or early termination
- The OL period at Visit 9 (Week 44), Visit 11 (Week 68) and Visit 14 (Week 104)/or early termination, for patients proceeding into OL period.

The following laboratory parameters (excluding those considered as efficacy parameters) will be classified as follows:

- Hematology:
 - Red blood cells and platelets: hemoglobin, hematocrit, red blood cell count, platelet count and hematocrit
 - White blood cells: white blood cell count, neutrophils, lymphocytes, monocytes, basophils, eosinophils.
- Clinical chemistry:
 - Metabolism: glucose, total protein, albumin, creatine phosphokinase (CPK),
 - Electrolytes: sodium, potassium, chloride, calcium, phosphorus, bicarbonate,
 - Renal function: creatinine, eGFR, creatinine clearance, blood urea nitrogen, uric acid,
 - Liver function: alanine aminotransferase (ALT), aspartate aminotransferase (AST), alkaline phosphatase (ALP), gamma glutamyl transferase (γGT), lactate dehydrogenase (LDH), total bilirubin, and in case of total bilirubin values above the normal range, must include conjugated and non-conjugated bilirubin (used for describing individual cases only).
- Adrenal gland hormones: cortisol (with reflexive adrenocorticotrophic hormone (ACTH) levels if cortisol < lower limit of normal [LLN]) and dehydroepiandrosterone sulfate (DHEAS).
- Gonadal hormones: testosterone (males) and estradiol (females).
- Pituitary hormones: luteinizing hormone (LH) and follicle-stimulating hormone (FSH).
- Fat soluble vitamins: A (retinol), D (25 hydroxy vitamin D), E (alpha-tocopherol), and K (phylloquinone).
- Serum pregnancy test: blood test at screening visit and local urine pregnancy test for all other tests.

Technical formulas are described in Section 2.5.1.

2.1.4.4 Vital signs variables

Vital Signs parameters include Heart Rate (HR), Systolic and Diastolic Blood Pressure (SBP and DBP) in sitting position, as well as weight, height and BMI.

Body weight was to be measured during:

- Run-in (if applicable) at Visit 1 (up to Week -6) or Screening at Visit 2 (up to Week -2).
- The double-blind period at Visit 4 (Week 0/Day 1), Visit 6 (Week 12), Visit 7 (Week 24)/or early termination.

• The OL period at Visit 8 (Week 32), Visit 9 (Week 44), Visit 11 (Week 68), Visit 13 (Week 92) and Visit 14 (Week 104)/or early termination for patients proceeding into OL period.

Height was to be measured during:

- Run-in (if applicable) at Visit 1 (up to Week -6) or Screening at Visit 2 (up to Week -2).
- The double-blind period at Visit 7 (Week 24)/or early termination.
- The OL period at Visit 9 (Week 44), Visit 11 (Week 68) and Visit 14 (Week 104)/or early termination for patients proceeding into OL period.

BMI and height percentiles will be calculated (1, 2, 3).

Heart rate and blood pressure were to be measured during:

- Screening at Visit 2 (up to Week -2).
- The double-blind period at Visit 4 (Week 0/Day 1), Visit 6 (Week 12), Visit 7 (Week 24) /or early termination.
- The OL period at Visit 8 (Week 32), Visit 9 (Week 44), Visit 11 (Week 68) and Visit 14 (Week 104)/or early termination for patients proceeding into OL period.

2.1.4.5 Electrocardiogram variables

Not applicable

2.1.4.6 Tanner stage measurement

Tanner stages measurement include assessments of boys–development of external genitalia, girls breast development, boys/girls –pubic hair, performed if possible, by the same investigator/designee trained to assess pubertal development, during:

- Run-in (if needed) at Visit 1 (up to Week -6) or Screening at Visit 2 (up to Week -2).
- The double-blind period at Visit 7 (Week 24)/or early termination.
- The OL period at Visit 9 (Week 44), Visit 11 (Week 68) and Visit 14 (Week 104)/or early termination for patients proceeding into OL period.

In addition, a global Tanner puberty classification as Prepubescent [Tanner stage = 1], Pubescent

[Tanner stage ≥ 2 to 4] and Postpubescent [Tanner stage = 5]) will be derived, based on breast development stage for girls and external genitalia stage for boys as it is commonly reported in the literature that in most children the first signs of puberty is breast development for girls and external genitalia for boys (4, 5, 6).

2.1.4.7 Cogstate battery test

Cogstate battery test was to be administered during:

- The double-blind period at Visit 4 (Week 0/Day 1) and Visit 7 (Week 24)/or early termination
- The OL period at Visit 11 (Week 68) and Visit 14 (Week 104)/or early termination

Cogstate battery test consists of identification test (IDN), detection test (DET), one card learning test (OCL), and Groton maze learning test (GML). The results (ie, scores) will be automatically calculated. The change from baseline to Week 24 will be calculated for each score.

Z-scores will be also computed for each test based on patient's age at baseline for the 24-week DB period, or based on patient's age at the visit when the test is performed for the OL period (see Appendix E and Appendix F for details).

A composite score will be calculated as the mean of the Z-scores equally weighted, provided that at least three of the four tests are available AND if all the following cognitive domains are covered:

- Attention, through either DET or IDN
- Visual learning, through OCL
- Executive function, through GML

Then change from baseline to Week 24 will be computed for the composite score.

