Appendix C Cogstate battery test

The Cogstate battery test will include a detection test, identification test, one card learning test, and Groton maze learning test. These individual tests assess maturing cognition across a broad number of key developmental functions such as processing speed, attention, visual learning and executive functioning, respectively. Details of the Cogstate battery test are provided in the description subsection below. Briefly, the battery of tests is administered by trained clinical site personnel and will take the patient approximately 16 to 19 minutes to complete. It will be administered electronically and is standardized. The results will be automatically calculated. The results will not be used for detection of adverse events and will not trigger further consultation or investigation.

Cogstate battery test description:

• Detection (DET; Psychomotor Function)

The Detection test is a measure of psychomotor function and uses a well-validated simple reaction time paradigm with playing card stimuli. In this test, the playing cards all depict the same joker. The subject is asked to press the **Yes** key as soon as the card in the center of the screen turns face up. The software measures the speed and accuracy of each response.

Duration of Test: 3 minutes

• Identification (IDN; Attention)

The Identification test is a measure of visual attention and uses a well-validated choice reaction time paradigm with playing card stimuli. In this test, the playing cards are all either red or black jokers. The subject is asked whether the card displayed in the center of the screen is red. The subject responds by pressing the **Yes** key when the joker card is red and **No** when it is black. The software measures the speed and accuracy of each response.

Duration of Test: 3 minutes

• One Card Learning (OCL; Visual Learning)

The One Card Learning test is a measure of visual learning and uses a well-validated pattern separation paradigm with playing card stimuli. In this test, the playing cards are identical to those found in a standard deck of 52 playing cards (without the joker cards). The subject is asked whether the card displayed in the center of the screen was seen previously in this test. The subject responds by pressing the **Yes** or **No** key. The software measures the speed and accuracy of each response.

Duration of Test: 6 minutes

• The Groton Maze Learning Test (GML; Executive Function)

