2.4.5.7 Analyses of Cogstate Battery test

Cognitive scores (including by domains: DET [Psychomotor Function], IDN [Attention]; [OCL; Visual Learning]; GML [Executive Function]) and composite score will be described on the safety population by treatment for the double-blind period.

The change from baseline will be described for each score and the composite score.

The absolute change from baseline in the composite score at Week 24 will be analyzed using an ANCOVA model, with unequal variances by treatment group (except if convergence issue). The model will include the fixed categorical effects of treatment group (alirocumab, placebo), the dosing regimen cohort (Q2W, Q4W), the treatment-by-dosing regimen cohort interaction, the randomization strata and the continuous fixed covariate of baseline composite score value. Model assumptions for normality will be explored prior to the analysis testing. Throughout the ANCOVA model, least-square (LS) mean and standard error (SE) will be provided for each treatment group (placebo, alirocumab) regardless of the dosing regimen cohorts. LS means difference will be provided for the comparison of the alirocumab group versus the placebo group regardless of the dosing regimen cohorts, with the SE, 95% confidence intervals (CI) for descriptive purpose, using

appropriate contrasts. The corresponding effect sizes will be computed using Cohen's formulae (see Appendix G).

For the OL period, the results will be described overall in the OL population.

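### The Cogstate composite change from baseline need not use the same tests at both visits, so it can move when no test score has changed

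*SAP*

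**What the plan says.** SAP 2.1.4.7 states: "A composite score will be calculated as the mean of the Z-scores equally weighted, provided that at least three of the four tests are available". A second condition is that three cognitive domains are covered. The three domain conditions are "Attention, through either DET or IDN", "Visual learning, through OCL" and "Executive function, through GML". The composite is the equally weighted mean of the available Z-scores. The section then adds: "Then change from baseline to Week 24 will be computed for the composite score". In the double-blind period both visits are standardised with norms for the patient's age at baseline, so an unchanged raw score gives an unchanged Z-score.

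SAP 2.4.5.7 fits an ANCOVA to the Week 24 composite change, with the baseline composite as covariate. It reports the LS mean difference with a 95% CI for description, and an effect size by the Cohen formula in Appendix G. Changes in the individual tests are summarised descriptively.

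Neither of these sections, nor SAP 2.5.3 on missing data, requires the two composites behind a change score to contain the same tests.

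On labels, SAP 2.4.5.7 has "DET [Psychomotor Function], IDN [Attention" and Protocol Appendix C has "The Detection test is a measure of psychomotor function". Protocol 11.4.3.3 agrees with both, and the Cogstate paragraph in Protocol Section 10 assigns DET to processing speed and IDN to attention.

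**The concern.** A change score should be zero when nothing has changed. Here the two composites can be averages of different tests. A patient who is weak on IDN relative to the other tests appears to improve if IDN is missing only at Week 24, and appears to decline if it is missing only at baseline. Adjusting for the baseline composite does not remove this, because that covariate may itself rest on a different set of tests.

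The composite change is the only Cogstate outcome with a model, an interval and an effect size. Protocol Section 4 names neurocognitive disorders as a potential risk to be monitored and Cogstate as the specific assessment of neurocognitive function. At stake is avoidable error in a paediatric safety summary, and a possible bias if missing tests are unevenly spread between arms.

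**Working it through.** The plan gives no power or precision figure for the composite, so there is none to reproduce. The check applies the rule directly.

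**Permitted sets.** OCL and GML are required, with DET or IDN or both. Three sets qualify: {DET, IDN, OCL, GML}, {DET, OCL, GML} and {IDN, OCL, GML}. Baseline and Week 24 therefore give 3 × 3 = 9 combinations. Three are matched and six are mismatched: four pair four tests with three, and two swap DET and IDN.

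**Shift when no Z-score changes.**
- Four tests to three: with m the mean of the three retained Z-scores and x the Z-score of the missing test, m − (3m + x)/4 = (m − x)/4.
- Swap of IDN for DET: (Z_DET − Z_IDN)/3.

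**Example.** Take the age-12 norms in SAP Appendix F, the Appendix E formula, and illustrative raw scores that are identical at both visits.

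| Test | Raw score | Norm mean (SD) | Sign | Z |
|---|---|---|---|---|
| DET | 2.52938 | 2.52938 (0.07682) | −1 | 0 |
| IDN | 2.78087 | 2.71368 (0.06719) | −1 | −1 |
| OCL | 1.02255 | 0.97878 (0.08754) | +1 | +0.5 |
| GML | 48.705 | 55.56 (13.71) | −1 | +0.5 |

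- All four at baseline: (0 − 1 + 0.5 + 0.5)/4 = 0.
- IDN missing at Week 24: (0 + 0.5 + 0.5)/3 = 0.333, a change of +0.333. The formula agrees: (0.333 + 1)/4 = 0.333.
- DET missing at Week 24 instead: (−1 + 0.5 + 0.5)/3 = 0, so no change, because DET happens to equal the mean of the other three.
- IDN only at baseline and DET only at Week 24: from 0 to 0.333, which is (0 + 1)/3.

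**Range of the shift.**

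| Gap (Z) | Four to three (gap/4) | DET/IDN swap (gap/3) |
|---|---|---|
| 0.5 | 0.125 | 0.167 |
| 1 | 0.25 | 0.333 |
| 2 | 0.5 | 0.667 |

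**Spread per affected patient.** Assume unit-variance Z-scores with common correlation r, which the documents do not give. The SD of the four-to-three shift is √(1 + (1 + 2r)/3 − 2r)/4.
- r = 0: √1.333/4 = 0.289
- r = 0.3: √0.933/4 = 0.242
- r = 0.5: √0.667/4 = 0.204
- r = 0.7: √0.4/4 = 0.158

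**Effect on the arm comparison.** The documents give no rate of single missing tests, so both figures below rest on assumed rates.
- Noise: the model pools the cohorts, with 100 alirocumab and 50 placebo patients planned. With a fraction f affected and artefact SD s, the contribution to the standard error of the difference, added in quadrature, is s√f × √(1/100 + 1/50). For f = 1% and s = 0.20 this is 0.20 × 0.1 × 0.173 = 0.003. For f = 5% and s = 0.29 it is 0.29 × 0.224 × 0.173 = 0.011.
- Bias: with a 1 Z gap in a consistent direction and a 10-point difference between arms in the share of mismatched patients, the mean shift is 0.25 × 0.10 = 0.025.

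**The case against.** The strongest reply is that little depends on this.

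- The battery is one electronic session of about 16 to 19 minutes, so a single test missing at a single visit may be rare.
- SAP 2.4.5 rules out formal inference on safety data, and SAP 2.4.5.7 presents the interval as descriptive. No decision rule depends on the composite.
- The individual test changes are reported beside the composite and cannot be distorted in this way, so a spurious movement could be checked against them.
- Neurocognitive harm is also captured through adverse events of special interest, with two prespecified term groupings in SAP 2.1.4.1. The protocol says Cogstate results will not be used to detect adverse events.
- The group-level figures above are small under the assumptions made.

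All of this stands, and it limits the importance of the point. It does not make the rule correct: the change score as defined can be non-zero for a patient whose scores are identical.

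A reader might also infer that the rule removes attention from the composite by dropping the only attention test. The documents do not support that. IDN is absent only when IDN itself is missing, and it stays when DET is missing. SAP 2.1.4.7 itself counts DET as covering attention. What remains is a conflict of labels between that section and SAP 2.4.5.7, Protocol Section 10, Protocol 11.4.3.3 and Protocol Appendix C.

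**Conclusion.** The point holds as a defect in the definition of the composite change. Six of the nine permitted combinations of test sets are mismatched, and in those the change can move with no change in any test. The shift is a quarter of the gap for four tests against three, with SD about 0.20 to 0.29 Z per affected patient for correlations of 0 to 0.5. It is a third of the DET–IDN difference for a swap. The unit variances and correlations are assumptions.

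The effect on the treatment comparison is probably small, and it cannot be sized from the documents because they give no missingness rate. If missingness is similar in both arms, the artefact mainly adds noise. A bias needs missingness that differs by arm.

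Two stronger readings should be avoided. The composite is not a formal test of neurocognitive harm whose conclusion is now unsafe, because the analysis is descriptive. Nor can the per-patient SD of 0.20 to 0.29 be set against the 0.2 cut-off for a trivial effect in Appendix G, because that cut-off applies to a group difference divided by a pooled SD.

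**What to change.** In SAP 2.1.4.7, define the composite change as the mean of the within-test Z-score changes over the tests available at both baseline and Week 24. Keep the minimum of three tests and the OCL and GML requirements. In SAP 2.4.5.7, compute the baseline composite covariate from the same common set. Report, by arm, the number of patients whose sets differed between visits. Unchanged scores then always give a change of zero; in the example, +0.333 becomes 0.

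The cost is a sentence or two of SAP text and a small programming change, with no new data. A patient with four tests at one visit and three at the other stays in the analysis. A patient with only DET at one visit and only IDN at the other has just OCL and GML in common and is dropped from the composite change. The baseline covariate also comes to depend on which tests are available at Week 24.

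Separately, reconcile the attention condition in SAP 2.1.4.7 with the sections that label DET psychomotor function or processing speed, for example by naming the condition psychomotor function or attention. IDN need not be made mandatory; that would exclude patients with valid DET, OCL and GML results.
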